Expiratory muscle function in critically ill ventilated patients

NTC:

Date of approved by METC: February 14, 2017

Date of amendment approved by METC: May 22, 2019

Rationale	
Inspiratory muscle weakness develops rapidly in ventilated critically ill patients¹⁻⁴ and is associated with adverse outcome, including prolonged duration of mechanical ventilation and mortality.⁵⁻⁷ Surprisingly, the effects of critical illness on expiratory muscle function have not been studied.
 
The main expiratory muscles are the abdominal wall muscles, including the external oblique (EO), internal oblique (IO) and transversus abdominis muscles (TRA).^{8,9} These muscles are activated when respiratory drive or load increases, which can be during e.g. exercise,¹⁰⁻¹² diaphragm fatigue,¹³ increased airway resistance, or positive airway pressure ventilation.¹⁴ The abdominal wall muscles are also critical for protective reflexes, such as coughing.¹⁵ Reduced abdominal muscles strength may lead to decreased cough function^{16,17} and thus inadequate airway clearance.¹⁸ This will lead to secretion pooling in the lower airways, atelectasis, and ventilator associated pneumonia (VAP).^{19,20} Studies have shown that decreased cough function is a risk for weaning failure and (re)hospitalization for respiratory complications.²¹ Further, high mortality was found in patients with low peak expiratory flow.²²
 
Considering the importance of a proper expiratory muscle function in critically ill patients, it is surprising that the prevalence, causes, and functional impact of changes in expiratory abdominal muscles thickness during mechanical ventilation (MV) for critically ill patients are still unknown.

------------------	--

Ultrasound is increasingly used in the ICU for the visualization of respiratory muscles. In a recent pilot study we confirmed the feasibility and reliability of using of ultrasound to evaluate both diaphragm and expiratory abdominal muscle thickness in ventilated critically ill patients (manuscript in preparation). An example of such measurement can be found in figure 1. Accordingly, the primary aim of the present study is to evaluate the evolution of abdominal expiratory muscle thickness during MV in adult critically ill patients, using ultrasound data.

Figure 1. Left: ultrasound of the abdominal expiratory muscles (EO, IO, TRA). Right: anatomical overview of the abdominal muscles. RA = rectus abdominis, less involved in respiration

Objective

Primary objective: to establish the effects of critical illness and mechanical ventilation on thickness of the abdominal expiratory muscles.

Secondary objectives:

- to establish the effect of changes in abdominal expiratory muscle thickness on the expiratory muscle function.

	
 - to establish the correlation between changes in thickness of the abdominal expiratory and inspiratory muscles. - to study whether changes in the thickness of the abdominal expiratory muscles also affects weaning outcome, and ICU readmission due to respiratory complications.
Study design	Prospective cohort study.
Study population	Patients who have been mechanically ventilated at the intensive care unit (ICU)
Inclusive criteria	
 - Age > 18 years - Invasive mechanical ventilation < 48 hours - Expected duration of mechanical ventilation > 72 hours
Exclusive criteria	
 - Past medical history of neuromuscular disorders - Mechanical ventilation > 48 hours within the current hospital admission - BMI > 35 kg/m² - Pregnant women - Open abdominal wounds at proposed location of the ultrasound probe, due to recent abdominal surgery
Sample size	100 subjects
Recruiting subjects	
Because mechanical ventilation is a requirement for eligibility, the participants frequently will be incapable of consent at the time of inclusion. Therefore, we will ask delayed informed consent from the patient as soon as he/she is capable of providing consent.
 
If patients are not able to give consent during their hospital stay, we will send an opt-out letter to the patient.

Intervention	Data from ultrasound measurements and from the electronic patient record will be obtained / analyzed. One additional blood sample will be obtained within 24 hours after inclusion, during planned blood collection (from arterial line or venous puncture).
Study endpoint	- Thickness of the abdominal expiratory muscles (external oblique, internal oblique, transverse abdominis muscle), during the inspiratory and expiratory phases of breathing.
Study parameters	
 - Thickness of the diaphragm muscle - Inflammatory markers (TNF-alpha, IL-6, IL-10) at inclusion (measured from blood sample using ELISA technique). - Respiratory function parameters: maximum inspiratory pressure (MIP), maximum expiratory pressure (MEP), cough peak flow (CPF), diaphragm pressure and diaphragm electrical activity (in selected patients with these measurements available in clinical practice). - Mechanical ventilation parameters. - Weaning outcome - Ventilator associated pneumonia (VAP) - Follow-up of 6 weeks: readmission to ICU / hospital, reason for readmission, pneumonia acquired after discharge when subject is hospitalized. - Critical illness parameters (e.g. medication, APACHE II score) - Patient characteristics (e.g. gender, age, neurological and cardiopulmonary co-morbidities, BMI) 
This data will be retrieved from the electronic patient record and anonymously filed in a database.
 
Data on muscle thickness (thickness of diaphragm muscle and expiratory muscles) will be collected directly

	from ultrasound measurements on the ultrasound device.
Statistical Analysis Plan	
SPSS statistical software package version 22.0 or R software for statistical computing version 3.2.0 will be used.
 
Primary endpoint: change of thickness of expiratory abdominal muscles during MV. Change in thickness will be presented as ratio change compared to baseline, to account for inter-subject variation in baseline thickness. The Wilcoxon signed-rank test will be used to compare changes in baseline and nadir values.
 
Association of categorical independent variables (such as sex, use of corticosteroids during ICU stay, sepsis on admission, etc.) with nadir change in expiratory muscle thickness will be assessed using a Mann-Whitney U test. Association of continuous independent variables (such as duration of mechanical ventilation, days taken to wean, inflammation at inclusion, etc.) with nadir change in expiratory muscle thickness will be assessed using a linear regression model, with change in expiratory muscle thickness as dependent variable. Correlation between change in thickness during the acute stage of MV (5 days) with the total time spent on the ventilator will be examined using a linear regression model.
 
Correlation between diaphragm and expiratory muscles
 
Correlation between change in expiratory muscle thickness and change in diaphragm thickness will be assessed with Pearson's correlation test to compare population means. The difference between change in

	
expiratory muscle thickness and change in diaphragm thickness will be assessed with a Student's t-test that is paired per subject. This will be done by using the change in thickness between baseline and the last data point obtained. Second, this will be evaluated by using the slope of the thickness curves assessed with a goodness of fit model. We will use a goodness of fit model to first describe the course of both diaphragm and expiratory muscle thickness for each subject. The type of model will be determined after data is obtained.
 
Subgroup analysis
 
Based on the outcomes of these analyses, a subgroup analysis may be performed to compare the subjects with high change in expiratory muscle thickness, to a group with low change in expiratory muscle thickness. A cutoff value to divide these groups will be determined based on how data will emerge. Variables as respiratory function measurements can be compared between groups with a Student's t-test, using group average values. Further, a Kaplan-Meier survival analysis will be carried out to quantify differences in time to wean between groups.

Referenties
	

- and endotracheal tube pressure with bilateral anterolateral magnetic phrenic nerve stimulation in patients in the intensive care unit. *Crit Care Med* 2001; 29:1325-31.

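### The cytokine value analysed as inflammation at inclusion may come from any time between 0 and just under 72 hours of ventilation, and the regression has no timing term: a minor, cheaply fixed weakness in an exploratory association

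*Combined protocol and SAP*

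**What the plan says.** All places are in the combined protocol and SAP.

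- **Inclusive criteria:** "Invasive mechanical ventilation < 48 hours". The matching exclusion, "Mechanical ventilation > 48 hours within the current hospital admission", confirms the limit.
- **Intervention:** "One additional blood sample will be obtained within 24 hours after inclusion, during planned blood collection (from arterial line or venous puncture".
- **Study parameters:** the result is listed as "Inflammatory markers (TNF-alpha, IL-6, IL-10) at inclusion (measured from blood sample using ELISA technique".
- **Statistical Analysis Plan, primary endpoint:** "Association of continuous independent variables (such as duration of mechanical ventilation, days taken to wean, inflammation at inclusion, etc" with nadir change "will be assessed using a linear regression model, with change in expiratory muscle thickness as dependent variable".
- **Same section:** "Change in thickness will be presented as ratio change compared to baseline".

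No section asks for the time of the draw or the hours ventilated at the draw, or names either as a covariate. Ventilator parameters are collected and total duration of ventilation is listed as a predictor, but neither is the time from start of ventilation to sample. The clock time of the baseline ultrasound is not stated.

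**The concern.** The label treats the marker as if every patient were sampled at the same stage of illness. The two windows together allow patients to differ by almost three days of ventilation. Two patients with the same inflammatory response, one sampled early and one late, enter the regression with different values if the markers move over that period.

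Two consequences are possible:

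- **Weakening.** Sampling time acts as measurement error in the predictor and pulls the correlation towards zero. This needs only that the markers change with time.
- **Confounding.** A patient included late has been ventilated longer before inclusion. If the baseline scan is done around inclusion and thinning is fastest early, part of that patient's loss precedes baseline and is not counted. If the markers are also falling, late inclusion lowers both the marker and the measured loss, and the two appear linked.

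At stake is the interpretation of the inflammation association. The Rationale lists the causes of thickness change among the unknowns, and this is the only blood sample the plan adds.

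**Working it through.** **Inputs from the documents.** Ventilation before inclusion: 0 to <48 h. Draw after inclusion: 0 to 24 h. N = 100. The plan gives N without alpha, power, effect size or SD, so it has no figure of its own to reproduce here.

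**Window.** <48 h + 24 h = just under 72 h.

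**Assumptions, none in the documents.** Inclusion is uniform on 0–48 h and the lag to the draw uniform on 0–24 h. ln marker falls linearly with time, at the same rate in all patients, with half-time 12, 24 or 48 h. Between-patient SD of ln marker is b = 1.0 or 2.0. Two-sided alpha is 0.05.

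**Spread of sampling time.** Var = 48²/12 + 24²/12 = 192 + 48 = 240 h², so SD = 15.5 h. The 24 h lag contributes 48/240 = 20% of the variance and inclusion time 80%.

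**Weakening.** Timing SD on the ln scale is s = (ln 2 / half-time) × 15.5. Ratio of observed to true correlation = b / √(b² + s²).

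| Half-time | s | Ratio, b = 1.0 | Ratio, b = 2.0 |
|---|---|---|---|
| 12 h | 0.895 | 0.75 | 0.91 |
| 24 h | 0.447 | 0.91 | 0.98 |
| 48 h | 0.224 | 0.98 | 0.99 |

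In power terms, N = 100 gives 81% power for a true correlation of 0.28 (Fisher z). In the worst cell this becomes 0.28 × 0.745 = 0.209, with 55% power. With a 48 h half-time power stays at 79–80%.

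**Confounding, model 1.** Simulation with N = 100 and no true link. With t0 the hours ventilated at inclusion, taken as the time of the baseline scan, and τ the time constant of thinning (48 to 120 h), measured loss = 20 points × [exp(−t0/τ) − exp(−(t0+120)/τ)] plus normal noise. The loss is read 120 h after baseline as a stand-in for the nadir. Unadjusted false-positive rates:

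| Setting | False positives |
|---|---|
| 12 h half-time, τ 48 h, b 1.0, noise SD 8 points | 62–65% across repeated runs |
| Same, noise SD 15 | about 24% |
| Same, b 2.0, noise SD 8 | about 29% |
| Same, b 2.0 and noise SD 15 | 11–13% |
| Slow kinetics | about 5% |

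With t0 as covariate the rate is about 5% (4–6%) throughout.

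**Confounding, model 2.** A linear version leaves 0 to 6 points of thinning per day before baseline unmeasured, with outcome SD 15. Unadjusted false positives are 4.7% to 17.4%, and stay near 5% when no early thinning is missed. After adding inclusion time and lag they are 4.6% to 5.5%.

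**The case against.** The strongest reply is that this is a small matter. Inflammation is in neither the primary objective nor any of the three secondary objectives. It is one example in an open list of predictors, and the primary signed-rank comparison of baseline with nadir does not use it. That stands, and it sets the weight of the point.

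A reader might infer that the plan will manufacture a link between inflammation and thinning, and might cite the top false-positive figure. The documents do not support that. A spurious link needs three things together: markers that fall with ventilation time, thinning concentrated in the first days, and a baseline scan tied to inclusion. None is stated. The Rationale says inspiratory weakness develops rapidly but treats changes in expiratory muscle thickness as unknown. The highest rate also needs a fast decline, a short time constant and small values of both SDs.

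A reader might also see a fault in the sampling scheme itself. Applying the 48 h criterion already requires knowing ventilation time at inclusion, and a routine draw probably carries a time in the patient record. The gap is therefore a covariate that the plan does not use and a label that is too precise. Weakening is also small outside the fast-decline corner.

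What survives is that the plan neither requires these times nor uses them. Without them, no one can adjust for timing or check whether it mattered.

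**Conclusion.** The point holds as a minor issue. The 0 to <72 h range, the label and the absence of a timing term are facts of the text. The consequences are conditional, because the documents give no marker kinetics, thinning rate or SDs. Weakening requires only that the markers change over the window, and runs from negligible to a loss of about a quarter of the correlation. Confounding is possible rather than shown, and its size, from none to large, depends wholly on assumed values. Both simulation models agree that adjusting for the recorded times restores the nominal error rate. That result rests on their assumption that ln marker declines linearly with time.

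**What to change.** - Record, from the routine record, the hours from start of ventilation to the blood draw and to the baseline scan.
- Enter them as covariates in the regression of nadir change on inflammation.
- Relabel the variable as inflammation sampled within 24 h after inclusion (0 to <72 h of ventilation) in Study parameters and the Statistical Analysis Plan.

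The cost is a few lines of SAP text, two time stamps and one or two degrees of freedom out of 100 patients. No extra blood is needed.

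Two other remedies add little. Restricting the analysis to draws within 24 h of the start of ventilation would keep only about 25 of 100 patients under the uniform assumption: (24²/2) / (48 × 24) = 0.25. Moving the draw to the first collection after inclusion would address only the lag, 20% of the timing variance.

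### No function, ventilator-time or weaning analysis adjusts for diaphragm change, so a diaphragm effect could be reported as an expiratory one

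*Combined protocol and SAP*

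**What the plan says.** All references are to the combined protocol and SAP.

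- **Objective.** Two secondary objectives are worded as effects of expiratory thickness: "to establish the effect of changes in abdominal expiratory muscle thickness on the expiratory muscle function", and "to study whether changes in the thickness of the abdominal expiratory muscles also affects weaning outcome, and ICU readmission due to respiratory complications". A third is to correlate the changes in the two muscle groups.
- **Rationale.** Inspiratory muscle weakness in these patients "is associated with adverse outcome, including prolonged duration of mechanical ventilation and mortality". The Rationale also gives an expiratory route: weak abdominal muscles impair cough, and poor cough raises the risk of weaning failure.
- **Study parameters.** Diaphragm thickness is measured by ultrasound. The function measures are listed as "Respiratory function parameters: maximum inspiratory pressure (MIP), maximum expiratory pressure (MEP), cough peak flow (CPF), diaphragm pressure and diaphragm electrical activity". The list does not say which of them answer the expiratory-function objective, and at least some are available only in selected patients.
- **Statistical Analysis Plan, diaphragm.** Diaphragm change enters a Pearson correlation with expiratory change, a paired t-test and a comparison of slopes.
- **Statistical Analysis Plan, outcomes.** A linear model is planned for "Correlation between change in thickness during the acute stage of MV (5 days) with the total time spent on the ventilator". Days to wean appears in a linear model that has expiratory change as the dependent variable. Patients may then be divided into high and low expiratory change at a cutoff chosen from the data: "Variables as respiratory function measurements can be compared between groups with a Student's t-test, using group average values", with Kaplan-Meier curves for time to wean. None of these names a diaphragm covariate, stratum or joint model.

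**The concern.** The plan names a rival explanation for longer ventilation, measures it in the same study, and sets out to learn how closely it moves with the exposure of interest. It then leaves it out of every analysis that links expiratory thickness to function, ventilator time or weaning.

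Suppose only the diaphragm matters for an outcome and the two muscles tend to thin together. Patients with marked expiratory thinning will then also tend to have marked diaphragm thinning, and the high and low groups will differ on that outcome for reasons unrelated to the abdominal muscles. Because the objectives are worded causally, the natural report would be that expiratory thinning worsens function or delays weaning. The planned correlation between the muscles would show whether this risk is present, but no later analysis uses that result.

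**Working it through.** **Inputs from the documents.** Sample size 100, with no alpha, power or effect size behind it, so there is no planned figure to reproduce. Exposure: expiratory change alone. Function test: two-group t-test. Weaning: Kaplan-Meier by the same groups.

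**Assumptions (the documents give none of these).** Correlation ρ between expiratory and diaphragm change: 0 to 0.7. Diaphragm effect b: 0.3 or 0.5, as a correlation for function and as a log hazard ratio per SD for weaning. True expiratory effect: zero. Cutoff: the median. Two-sided alpha 0.05. For weaning, a log-rank test without censoring.

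**Spurious group difference.** With standardised normal variables, a median split gives an expected difference of 2·√(2/π)·ρ·b = 1.596·ρ·b SD.
- ρ = 0.3, b = 0.3: 1.596 × 0.09 = 0.14 SD
- ρ = 0.5, b = 0.5: 1.596 × 0.25 = 0.40 SD
- ρ = 0.7, b = 0.5: 1.596 × 0.35 = 0.56 SD

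With 50 against 50, the standard error is about √(2/50) = 0.20 SD. The middle case has z = 0.40/0.20 = 2.0, so about half of studies would reject. For scale, 50 against 50 has 80% power at 0.56 SD, so at the top end the spurious difference is about as large as the study could detect.

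**Simulation, n = 100, 4,000 studies per setting.** Percentage declaring an expiratory effect (b = 0.3 / b = 0.5):

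| ρ | t-test, median split | Log-rank, time to wean | Linear model with both muscles |
|---|---|---|---|
| 0 | 4.6 / 5.4 | 5.3 / 5.3 | 5.1 / 5.6 |
| 0.3 | 11.0 / 20.1 | 11.2 / 17.4 | 5.1 / 4.7 |
| 0.5 | 21.4 / 49.8 | 19.8 / 39.7 | 4.9 / 5.0 |
| 0.7 | 38.9 / 80.9 | 34.9 / 66.6 | 4.9 / 4.9 |

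A second simulation of the t-test gave 11% to 82% over ρ 0.3 to 0.7, and 52.5% at 0.5/0.5. If only 50 patients had function data (assumed), the t-test range is 8% to 51%. Treating expiratory change as continuous, which is closer to the ventilator-time regression, gives 14% to 95% at n = 100, with ventilator time simulated as a normal variable.

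**Time to wean with adjustment.** A Cox model (600 studies per setting, no censoring) gave 15% to 85% with expiratory change alone and 4% to 7% with diaphragm change added.

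**Error in the diaphragm reading.** With reliability λ, the expiratory coefficient left after adjustment is ρb(1−λ)/(1−ρ²λ). At ρ = 0.7, b = 0.5, λ = 0.8 this is 0.35 × 0.2/(1 − 0.392) = 0.12, against 0.35 unadjusted. Across the range, the simulated false-positive rate in the linear model is about 5% to 17% at λ = 0.8 and 6% to 44% at λ = 0.6.

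**Price of adjustment.** Variance inflation is 1/(1−ρ²): 1.10, 1.33 and 1.96 at ρ = 0.3, 0.5 and 0.7. The standard error rises by the square root: 1.05, 1.15 and 1.40 times.

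**The case against.** **The outcomes are not mainly diaphragm outcomes.** A reader might infer from three inspiratory items out of five that they are. The documents do not support that: MEP and CPF are both listed, the Rationale calls the abdominal muscles essential for cough, and it gives a cough route to weaning failure. Nor does the plan combine the five measures or say that MIP will be reported as expiratory function. What stands is that the outcome for the expiratory-function objective is not named.

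**The plan does compare the two muscles.** It correlates them, tests their difference and compares slopes. This stands. The gap is narrower: nothing separates them with respect to outcome.

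**No claim of an independent expiratory effect is made.** A reader might take the weaning objective to promise an effect over and above the inspiratory muscles. The documents do not say so. The gap they set out to fill is the unknown prevalence, causes and functional impact of expiratory thickness change. An observational cohort may report unadjusted associations, provided they are described as such; the causal wording of these objectives is what makes the omission matter.

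**The rates are built on assumptions.** This is true. The correlation is an open question in this study. The Rationale notes that abdominal muscles are activated during diaphragm fatigue, so opposite movement is possible; the spurious difference would then change sign.

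**Weight.** The high/low comparison is optional and the primary aim is to describe thickness. But the regression of early change against ventilator time is not optional, and it has the same gap.

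**Conclusion.** The point holds in this form: no function, ventilator-time or weaning analysis adjusts for or stratifies by diaphragm change, although it is measured and the Rationale names inspiratory weakness as a correlate of long ventilation. The consequence depends on a correlation nobody yet knows. At zero there is no bias. At an assumed 0.3 to 0.7, with an assumed diaphragm-outcome correlation of 0.3 to 0.5 and all 100 patients contributing, a false expiratory effect on function appears in about 11% to 82% of studies at a median split. Adjustment removes nearly all of this only if diaphragm change is read without error.

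It would go too far to say that the plan will mistake diaphragm loss for expiratory loss. The documents show only that it could not tell them apart with respect to outcome. The primary description of expiratory thickness is untouched. This is a cheap improvement to the secondary analyses, worth making before the data are analysed.

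**What to change.** 1. **Ventilator time.** In the 5-day analysis, make ventilator time the outcome and enter expiratory and diaphragm thickness change over the same window.
2. **Time to wean.** Alongside the Kaplan-Meier curves, fit a time-to-event regression with both changes.
3. **Reporting.** Show the expiratory coefficient with and without the diaphragm term, and base any statement specific to the expiratory muscles on the joint model.
4. **Function.** For the expiratory-function objective, name MEP and then CPF as outcomes, with diaphragm change as a covariate where numbers allow. Report MIP, diaphragm pressure and diaphragm electrical activity separately, as inspiratory measures.

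The cost is SAP wording; diaphragm thickness is already collected. The expiratory coefficient becomes less precise (variance 1.1 to 2.0 times for correlations of 0.3 to 0.7), and error in the diaphragm reading leaves some residual confounding, which the report should acknowledge. Function data limited to selected patients may leave too few for a joint model; the report should then describe the result as an unadjusted association.

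### Nothing masks whoever reads muscle thickness to study day, clinical data or the other muscle's result, so the primary within-patient change is open to expectation bias that masked reading of stored images would reduce

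*Combined protocol and SAP*

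**What the plan says.** All references are to the combined protocol and SAP.

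- **Study parameters.** After listing the clinical variables, the plan gives their source: "This data will be retrieved from the electronic patient record and anonymously filed in a database". It then gives the source for thickness: "Data on muscle thickness (thickness of diaphragm muscle and expiratory muscles) will be collected directly" and, completing the sentence, "from ultrasound measurements on the ultrasound device".
- **Intervention.** The only other description of data collection is "Data from ultrasound measurements and from the electronic patient record will be obtained / analyzed".
- **Study design and Study endpoint.** The design is a "Prospective cohort study". The endpoint is "Thickness of the abdominal expiratory muscles (external oblique, internal oblique, transverse abdominis muscle), during the inspiratory and expiratory phases of breathing".
- **Statistical Analysis Plan.** The primary endpoint is "change of thickness of expiratory abdominal muscles during MV", expressed as a ratio to baseline. "The Wilcoxon signed-rank test will be used to compare changes in baseline and nadir values". Nadir change is then related to factors such as sepsis, corticosteroid treatment and time on the ventilator. Change in the expiratory muscles is also correlated with, and compared by paired t-test to, change in the diaphragm.
- **Rationale.** A pilot is said to have shown that the ultrasound method is feasible and reliable. No figures are given.

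No section mentions masking, coded images, reading order, an independent reader or repeat readings.

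**The concern.** Placing calipers on a thin muscle layer is a judgement. If the reader knows that a scan is a late one, or that the patient is septic or failing to wean, the placement can drift in the expected direction without any intent.

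Three features of the study make this matter:

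1. The primary result is a within-patient change. A shift that is absent at baseline and present later is indistinguishable from thinning.
2. There is one cohort and no control arm, so a time-related reading shift has no counterpart to cancel against in the primary test.
3. The same change values feed the association analyses and the diaphragm comparison. A shift that depends on clinical state could create or strengthen an association. Shared reading errors across the two muscle groups could raise their correlation.

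Reliability in the pilot does not settle this. A reader can be highly repeatable and still shift systematically once the study day is known.

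**Working it through.** The plan has no figure to reproduce on this point. Its sample size of 100 comes without alpha, power, effect size or standard deviation, and the point does not dispute it.

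**Step 1: what the text settles.**

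| Question | Answer in the documents |
|---|---|
| Source of thickness values | Measurements on the ultrasound device |
| Who scans, who places the calipers | Not stated |
| Live, or later from stored images | Not stated |
| Reader's knowledge of day and clinical data | Not stated, and nothing restricts it |
| Diaphragm and abdominal muscles read separately | Not stated |
| Masking or random reading order | None |

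Following the plan as written therefore permits fully unmasked reading.

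**Step 2: how a shift translates into change.** Apparent change = caliper shift ÷ layer thickness. Both inputs are assumptions; the documents give neither.

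| Assumed shift | 3 mm layer | 5 mm layer | 8 mm layer |
|---|---|---|---|
| 0.2 mm | 0.2/3 = 6.7% | 0.2/5 = 4.0% | 0.2/8 = 2.5% |
| 0.3 mm | 0.3/3 = 10.0% | 0.3/5 = 6.0% | 0.3/8 = 3.8% |

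**Step 3: does n = 100 help?** No. The standard error of the mean change is SD/√100 = SD/10, but the bias b stays at b. With no true change, the chance of a significant result is approximately Φ(b/(SD/10) − 1.96) + Φ(−b/(SD/10) − 1.96). For b = 2 and SD = 10 percentage points this is Φ(2 − 1.96) + Φ(−2 − 1.96) = 0.516. Simulating the signed-rank test itself (2,000 studies per setting, normal data, two-sided 0.05, all assumed) gives:

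| Assumed under-reading of later scans | SD 5 | SD 10 | SD 15 | SD 20 |
|---|---|---|---|---|
| None | 5% | 5% | 5% | 5% |
| 2% of baseline | 96% | 49% | 25% | 15% |
| 5% of baseline | 100% | 100% | 89% | 68% |

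A small shift would matter if it occurred. The table does not show that one occurs.

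**Step 4: what masked reading would leave untouched.** Suppose there is no reading bias and no true change, but the lowest of k follow-up scans is compared with baseline (1,000 simulated studies per setting; k and the random error SDs of 3%, 5% and 10% are assumed). With k = 1 the test is significant in 4–5% of studies. With k = 2 it is significant in 98–99%, and with k = 4 or 6 in 100%. For k = 4 the mean spurious change is about −3%, −5% and −10% for the three error SDs. Masking does not address this.

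**The case against.** The strongest reply is that the plan is silent on reading and that silence does not show a faulty procedure. Much of that stands.

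- **Live reading by an informed operator.** A reader might infer that calipers are placed at the bedside by someone who can see the day, treatment and condition. The documents do not support this as fact. The sentence follows one about the patient record, so its evident purpose is to name a data source, and measurements on a device can be made later from saved images.
- **One operator, one session.** A reader might infer that diaphragm and abdominal muscles are measured together by the same person. Neither operator nor session is described.
- **An expectation of thinning.** No directional hypothesis is stated; the aim is to describe how thickness evolves. The comparison with the nadir points towards thinning, but only as a hint.
- **Internal comparisons.** A proportional shift equal in all patients largely cancels in the Mann-Whitney comparisons, and one equal in both muscle groups largely cancels in the paired t-test. To create an association, the shift must differ by exposure, and nothing in the documents sizes that. Total ventilator time is also not yet known at the early scans of patients who are still ventilated.
- **Masking as a cure.** It is tempting to say that masked reading would remove the bias. It would not: probe position, probe pressure and the choice of frame to store stay unmasked, and the nadir problem in Step 4 is untouched.

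None of this closes the gap. Nothing prevents unmasked reading, and the primary test is exposed to a common shift whether or not the secondary comparisons are. Masked reading would also still protect analyses that do not use the nadir, such as those of early change, change to the last data point and slopes.

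**Conclusion.** The point holds as a gap in safeguards, not as a demonstrated bias. The plan takes every thickness value from measurements on the device and provides no masking for a judgement-based primary measurement in a single cohort. A systematic shift between baseline and later scans would enter the primary result in full and would not diminish with sample size.

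Its real size is unknown. The 2.5% to 10.0% range rests entirely on assumed shifts of 0.2–0.3 mm and assumed layers of 3–8 mm, and the rejection rates rest on assumed bias and SD. Effects on the associations and on the diaphragm correlation need the further assumption that the shift varies with exposure, or is shared between the two muscle groups and varies between patients. The safeguard is inexpensive and should be adopted. It is not a condition on which the study stands or falls, and it does not replace dealing with the nadir separately.

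**What to change.** Amend Study parameters and the Statistical Analysis Plan to state who scans and who reads, and add the following:

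1. At each scan, save still images or clips under a code that hides patient identity and scan date.
2. The same investigator measures thickness later from the coded images in random order, without access to clinical data. Diaphragm and abdominal images are read in separate batches.
3. All analyses use these masked readings. A bedside value is kept only where no image was stored, and is flagged as such.
4. State in the report that acquisition (probe position, pressure, choice of frame) was unmasked.

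**Cost.** A short amendment, image storage, a coding step and offline reading time. No extra scan, patient burden or second reader is needed. One weakness of using the same investigator is that some images may be recognised; coding and random order limit this but do not exclude it.
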